control group (stopwatch will be used). Pain score (Neonatal Infant Pain Scale) and parental satisfaction survey will be filled at the time of the procedure.

Outcome: Contamination rate and feasibility of both urine sampling techniques

3. Introduction: literature review and justification of the study.

Urinary tract infection (UTI) is a common source of infection in children. It accounts for 5 to 14 percent of visits by children every year [1]. The overall prevalence is around 7% among different age subgroups of children. Several factors affect the prevalence of UTI including age, gender, and circumcision status [2].

The diagnosis of UTI requires obtaining a urine specimen from the patient. Generally, there are four methods used in collecting urine samples which can be categorized as invasive (such as suprapubic aspiration and urethral bladder catheterization) and noninvasive (such as Sterile bag and clean catch) [3].

The selection of the urine collection technique is mainly determined by whether the patient is toilet-trained or not. In non-toilet-trained patients, urethral bladder catheterization or suprapubic aspiration can be used. The latter is having the least contamination rate in urine culture [3]. Clean-catch urine is commonly used for toilet-trained patients. If the clinical assessment of febrile infants necessitates immediate antimicrobial therapy, urine culture should be obtained either by urethral bladder catheterization or suprapubic aspiration [3, 4].

Previous observational studies showed approximately a 1 percent contamination rate using the suprapubic aspiration technique [5,6,7,8,9]. In a prospective study done on premature infants it was found that the suprapubic aspiration technique resulted in increased pain and a higher probability of procedural failure compared to urethral bladder catheterization [10]. According to American academy of pediatrics (AAP), for non-toilet trained children, it's advisable to gather a urine sample through methods like ureteral catheterization or suprapubic bladder aspiration, especially when a sample obtained using a perineal bag shows positive results on a dipstick test [11]. The latest guideline from AAP recommends urine culture to be obtained via either SPA or bladder catheterization in pediatric patients aged between 8 to 60 days old, due to false positive results that can occur in the other urine collection techniques [12].

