Urethral bladder catheterization carries a 6 to 12 percent of contamination rate. In regard clean catch urine method 16 to 63 percent of the contamination rate [2].

As outlined in the guideline in National Institute for Health and Care Excellence (NICE) guideline, to use clean catch urine wherever possible in pediatric patients below 16 years old. And to reserve bladder catheterization and suprapubic aspiration when noninvasive methods are not possible or practical [13].

Herreros et al. demonstrated a safe and noninvasive technique to collect midstream clean-catch urine in infants. It was based on bladder stimulation and paravertebral lumbar massage [14]. This technique yielded accurate and low contamination rates for infants below 90 days old. Moreover, the success rate was 86.3 percent, while the contamination rate was 5 percent. Nilgun et al. emphasized the safety and efficacy of the same stimulation technique in a neonatal intensive care unit setting. The median time to collect urine was 64 seconds. The success rate is 90 percent. However, Labrosse et al. showed a lower success rate reaching 61 percent, possibly due to patients with a low oral intake that were not excluded from the study [6,15].

In the effort to reduce bladder catheterization in children, different techniques were introduced in the previous literature to improve the clean catch urine success rate as well as the contamination rate [6,14,15,16]. Bladder and lumbar paravertebral massage maneuvers as described by Herreros et al are a safe, time-saving technique that needs to be studied further.

In our setting, the recommendations from international guidelines are being followed. For non-toilet trained children suspected to have UTI, initial urine specimen for urine dipstick is collected by sterile bag or bladder catheterization. If the result of the urine dipstick came positive, then urine culture is obtained via bladder catheterization, if the initial specimen collected by the sterile bag. In addition, we lack the statistics of urine culture contamination in our laboratories.

The main aim of this study is to introduce clean catch urine (bladder massage technique) to our setting, and to compare its feasibility with the bladder catheterization which is the standard practice.

4. Objectives and hypothesis of the study:

Primary outcome:

To compare the contamination rates between the two method and parent satisfaction.

Secondary outcome:

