To compare procedure duration in both methods. And pain score (using neonatal infant pain scale)

Study hypothesis

- The contamination rate of clean catch urine sampling is similar to the bladder catheterization.
- Less painful as it is less invasive.

5. Feasibility of the study

It is a multicentered study which enrolls pediatric patients who need urine collection according to the mentioned inclusion criteria. Notably, urinary tract infection (UTI) is a very common presentation in this age group, and it should be considered in almost all pediatric patients with fever with no clear source of infection. All the previously mentioned points can assure that the targeted sample size can be achieved within the designated timeline.

6. Research Design and Methods

Study design:

This pilot study will be conducted as randomized controlled trial.

Characteristics of study area and target population:

Study will be conducted in a tertiary hospital, pediatric emergency, and pediatric ward. Target population are pediatric patients aged between 0 to 6 months.

Primary and secondary endpoints:

Primary endpoints: Urine culture contamination rate and parental satisfaction

Secondary endpoints: Pain score (utilizing Neonatal Infant Pain Scale) and duration of the procedures.

Selection and withdrawal of subjects:

All infants younger than 6 months of age, who require urine sample as part fever work-up in emergency department.

Any subject may be withdrawn from the study at any time for any reason and without penalty or prejudice.

Sampling and sample size:

A pilot study with 40 samples in each arm will be conducted since there is no prior information about contamination rates in our local setting.

7. Randomization

The study will utilize computerized block randomization technique to assign participants into experimental and control groups, with each block being randomized to ensure unbiased allocation. The randomization will occur in the emergency triage.

8. Study flow

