Patient will be assessed in triage and cases to be included in the study as per the inclusion criteria, after that patients will be randomized using computerized block randomization technique into two groups. Then, patients will be assigned to a bed, pulse oximetry to be applied, data collection sheet to be filled, confirm that infant had good feeding/ didn't pass urine over last 20 minutes and proper cleaning to be done. The next step will be, collecting urine sample according to randomization group. Group A patients (control group), urine to be collected by standardized catheterization technique while group B by standard CCU technique. Meanwhile, time of each procedure to be documented. Regarding group B , after collecting urine by CCU , we recommend to collect another sample by catheterization to guide the management and antibiotic choice. (Appendix: Study flow chart)

9. Study procedures

Clean catch urine (bladder massage technique) provided in the appendix.

10. Variable definitions and measurements

Data collection tools and methods: (provided in the appendix)

Data quality:

In each site there will be a focal point doctor, responsible for the site. Before conducting the study, we will do training sessions about the study and we will prepare a video teaching the physicians/ nurses the steps of urine collection of by clean catch technique. Individual meetings to be conducted with the focal point for each site to clarify their inquiry. We will use a research assistant for data collection to facilitate the process and to help monitoring the flow of the study protocol.

Data analysis: We will use Statistical Package for the Social Sciences (SPSS) applications version 25 for our analysis.

11. Ethical considerations

Already we have the ethical approval from the ministry of health of Oman (proposal ID: MoH/CSR/23/26368), all recommended changes were adjusted before starting the study. If any risk on patient safety noticed during our study, we will make sure to stop the study protocol. We are not anticipating any harm to patient as the technique our study introducing is less invasive and more comfortable to patients. For the patient group with CCU collection, we are recommending another sample of urine to be collected to guide the antibiotics choice as CCU contamination rate and accuracy will be studied by this paper.

12. Conflict of interest

No conflict of interest

13. Incentives

No incentives of any kind will be given to the participants.

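### Febrile infants needing immediate antimicrobials are randomized with no visible exception, and the clean-catch arm does not ensure a catheter culture before the first antibiotic dose

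*Protocol*

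**What the plan says.** **Who enters and when.** Section 6 (Selection and withdrawal of subjects) admits "All infants younger than 6 months of age, who require urine sample as part fever work-up in emergency department". Section 7 adds: "The randomization will occur in the emergency triage". Section 8 gives the order: check of inclusion criteria at triage, randomization, preparation, then collection by the allocated method. No exclusion criteria appear in the text shown. The study flow chart that section 8 refers to is not shown.

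**What the protocol says about urgent infants.** The background in section 3 states: "If the clinical assessment of febrile infants necessitates immediate antimicrobial therapy, urine culture should be obtained either by urethral bladder catheterization or suprapubic aspiration". It also cites a guideline asking for the same two methods at 8 to 60 days, an age band inside the eligible range. The same section cites another guideline that prefers clean catch wherever it can be done.

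**The catheter sample in the clean-catch arm.** Section 8: "after collecting urine by CCU , we recommend to collect another sample by catheterization to guide the management and antibiotic choice". Section 11: "we are recommending another sample of urine to be collected to guide the antibiotics choice", without naming the method. The arm letters differ between sections 2 and 8, but the recommendation plainly concerns the clean-catch arm.

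**Other provisions.** Section 6 allows withdrawal at any time. Section 11 has a general clause to stop if a safety risk is seen. Section 19 hands an infant with a failed clean catch to the treating doctor. The data collection sheet asks whether antibiotics came before or after each type of collection.

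**The concern.** The protocol reports a culture standard for infants who need treatment at once and then writes eligibility, randomization and study flow without reference to it. The second catheter sample covers much of the ground, but three gaps remain for an urgent infant allocated to clean catch:

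1. The sample is advised, not mandatory.
2. It is placed after the clean-catch attempt. After a failed attempt, no culture is specified.
3. Nothing says it must precede the first antibiotic dose.

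What is at stake is the culture that guides treatment. Without a pre-dose catheter sample, the clinician may have only a clean-catch culture, whose contamination and accuracy section 11 says this study is to examine, or a catheter culture taken after antibiotics have started. The before/after item on the data sheet would show the order of events but not the length of any delay.

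**Working it through.** The protocol states no figure on this point, so there is nothing to reproduce. The check follows an urgent infant through the text and then asks what the quoted figures can and cannot size.

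**Path through the text for an urgent infant allocated to clean catch**

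| Step | Section | Rule for urgent infants? |
|---|---|---|
| Eligibility | 6 | None visible |
| Randomization at triage | 7, 8 | None visible |
| Clean-catch attempt | 8, appendix | None visible |
| Catheter sample afterwards | 8, 11 | Recommended; no timing against antibiotics |
| Failed attempt | 19 | Treating doctor's plan; no culture named |
| Antibiotic timing | Data sheet | Order recorded, none required |

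A course that meets every step can end with antibiotics given and no earlier catheter culture.

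**Time to the end of the clean-catch attempt.** Inputs: stimulation starts 25 minutes after feeding and success is judged at 5 minutes (appendix, clean catch technique); a quoted median collection time of 64 seconds (section 3).
- Already fed 25 minutes earlier: 64 / 60 = 1.07 minutes.
- Fed only after allocation, full attempt: 25 + 5 = 30 minutes.

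Cleaning and set-up are not included. No catheter-arm time is given, and section 8 lists the feeding check and cleaning before the arm-specific step for both groups. A between-arm difference cannot be formed.

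**Attempts with no specimen.** From the success rates in section 3, with 40 per arm:
- 1 − 0.90 = 10.0%; 0.100 × 40 = 4.0 infants.
- 1 − 0.863 = 13.7%; 0.137 × 40 = 5.5 infants.
- 1 − 0.61 = 39.0%; 0.390 × 40 = 15.6 infants. This is a pessimistic bound: that study did not exclude low oral intake, whereas section 8 checks feeding.

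**Contamination if only the clean-catch culture exists.** Section 3: "Urethral bladder catheterization carries a 6 to 12 percent of contamination rate"; for clean catch in general, "16 to 63 percent of the contamination rate"; for one study of the massage technique, "the success rate was 86.3 percent, while the contamination rate was 5 percent". Clean catch minus catheter:
- General figures: 16 − 12 = +4 to 63 − 6 = +57 points.
- Massage-study figure: 5 − 12 = −7 to 5 − 6 = −1 points.

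The sign depends on which figure applies.

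**Urgent share (assumed; the protocol gives none).** For a share s of otherwise eligible infants, clean-catch infants exposed to the gap = 40s, and infants screened to randomize 80 = 80 / (1 − s).

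| s | Exposed, of 40 | Screened for 80 |
|---|---|---|
| 0.05 | 2 | 84.2, so 85 |
| 0.20 | 8 | 100 |
| 0.50 | 20 | 160 |

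Exposed means open to the gap, not harmed.

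**The case against.** The strongest reply is that the safeguard already exists. Sections 8 and 11 call for a second sample precisely to guide antibiotic choice, and when it is taken by catheter before treatment, the section 3 standard is met. The clinician also has permitted ways round the problem: a short attempt followed by a catheter sample and then antibiotics, or withdrawal and immediate catheterization. Nothing holds antibiotics back. Local practice as described in section 3 already allows a sterile-bag specimen first, with catheter culture after a positive dipstick. The section 3 sentence is literature background, not a trial rule. The flow chart is not shown and may carry an exclusion.

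Much of this stands, and it rules out several stronger readings that a reader might infer:

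- *The protocol breaks a rule of its own.* It does not. The sentence is background, another cited guideline leans the other way, and the recommended sample largely satisfies it.
- *The trial delays antibiotics, by up to 30 minutes in the clean-catch arm.* The text withholds no treatment. The 30 minutes assumes feeding begins after allocation, and preparation time may be common to both arms.
- *Urgent infants would be treated on a worse culture.* The quoted contamination figures do not settle even the direction.

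What does not stand is that the gap is thereby closed. Withdrawal and the stop clause act after allocation and give no instruction for an urgent infant. The local bag-first route is not described for urgent infants and still ends in a catheter culture after a positive dipstick. A recommendation with no timing leaves a pre-treatment catheter culture to chance.

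**Conclusion.** The point holds as a gap in the written procedure. The protocol randomizes urgent febrile infants with no visible exception and does not ensure a catheter culture before the first antibiotic dose in those allocated to clean catch. It should be fixed, because it concerns safety and the remedy is short.

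No size of harm can be given. The lead times, failure rates and contamination ranges describe what could happen under the quoted sources, and the exposure counts rest entirely on assumed urgent shares. If clinicians always take the recommended catheter sample before dosing, the residual risk is small. Confidence is moderate, chiefly because the flow chart could contain an exception.

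**What to change.** 1. **Eligibility.** At triage, before randomization, identify infants judged to need immediate antimicrobials. Do not randomize them, and obtain their culture by catheter. A screen at this point applies equally to both arms.
2. **Randomized clean-catch infants who then need antibiotics.** In sections 8 and 11, change the recommendation to a requirement: a catheter culture before the first dose, without holding treatment for the clean catch.
3. **Analysis.** Keep these infants in their allocated arm. Report clean catch not attempted or not obtained for this reason as a separate category, and align section 19 with this. Dropping them, or leaving them out of the count, would be a one-arm exclusion after randomization based on clinical judgement, and would distort the feasibility result.
4. **Data sheet.** Keep the before/after item. Add clock times for randomization, each specimen and the first antibiotic dose, so that any delay can be measured.

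**Cost.** A few sentences and time fields. Accrual slows by an unknown amount: 85, 100 or 160 infants screened for 80 randomized at assumed urgent shares of 5%, 20% and 50%. Section 16 already names sample size as a difficulty. Results would apply to infants not needing immediate antibiotics, and a few clean-catch specimens may be lost.

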14. Results Dissemination

The study results will be disseminated through various channels to ensure wider reach and maximum impact. This includes local and international publication of the

study in peer-reviewed journals, as well as presentation of findings at relevant conferences and symposiums. Additionally, we plan to share the study outcomes with relevant stakeholders such as healthcare professionals, policymakers to ensure that the findings are effectively translated into practice and policy.

15. Management and monitoring of the research activities

Each focal point will be responsible for that hospital work flow. As each focal point will be in direct contact with the workers at the specific site. Daily monitor to be done to check the new enrolled cases. The other researchers to follow the whole workflow weakly by contact the assigned focal point.

16. Limitations and difficulties of the study:

1. Constrained timeframe for research due to residency program obligations
2. Ensuring an adequate sample size

17. Rationale for subject selection and recruitment.

This is a randomized control study, aiming to study the feasibility and contamination rate of urine collected by clean catch technique comparing to catheterization technique. The population enrolled in this study, pediatric patients, that will benefit of introducing clean catch technique. This is a population who cannot give urine sample for laboratory testing without catheterization which is a painful procedure. The clean catch technique will be of much help for this age group as it is painless and less invasive technique. Therefore, it seems highly beneficial to study the contamination rate of CCU collection in order to introduce it in local guidelines to replace the current use of catheterization.

18. Statistical analysis:

For data entry purposes Microsoft Excel software will be used and for the data analysis IBM SPSS statistics will be used. Normally distributed continuous data will be analyzed using student T test, if abnormal MANN-WHITNEY test will be used. For categorical comparisons CHI-square test will be applied. P-value of less than 0.05% will be considered as statistical significance.

19. Criteria for terminating the study.

A subject who is included in the study, and failed urine collection by CCU , will be removed from study and counted as CCU collection failure. After that to be managed by in-charged doctor as per the treating doctor plan.

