- I have read the foregoing information, or it has been read to me. I have had the opportunity to ask questions about it.
- Any questions that I asked, they have been answered to my satisfaction. I consent voluntarily to participate as a participant in this research.

Authorized to consent name:

Relationship to the patient:

Signature date:

Researcher/Doctor:

Clean catch urine technique

Clean catch urine (bladder massage technique)

- Two people (trained nurses and/or physicians) were needed to perform the procedure, and a third to measure the time taken. This technique involves a combination of fluid intake and non-invasive bladder stimulation maneuvers .
- To provide breast-feeding or formula intake appropriate to the age and weight of the newborn. In babies fed infant formula, 10 ml was provided on the first day of life, increasing to 10ml per day during the first week. From the second week onwards, 25 ml/kg were administered before the onset of stimulation .
- Twenty-five minutes after feeding, the infant's genitals were cleaned thoroughly with warm water and soap and dried with sterile gauze .
- A sterile collector was placed near the baby to avoid losing urine samples.
- Hold the baby under their armpits with their legs dangling. One examiner then starts bladder stimulation which consists of a gentle tapping in the suprapubic area at a frequency of 100 taps or blows per minute for 30 seconds .
- Stimulation of the lumbar paravertebral zone in the lower back with a light circular massage for 30 s. Both stimulation maneuvers are repeated until micturition starts, and a midstream urine sample can be caught in a sterile collector.
- Success is defined as the collection of a sample within 5 min of starting the stimulation maneuvers.

Definitions for UTI, contamination, and insignificant growth

Urine culture results			
Definition	Urinalysis result	Organism(s) Cultured	Colony Threshold ^a
No growth	Negative	No growth	No growth
UTI	Positive ^b	1 Uropathogen ^c	≥100,000 CFU/mL
	Positive	1 Uropathogen	10,000–100,000 CFU/mL ^d
Contaminated	Negative	1 Non-uropathogen	≥100,000 CFU/mL
	Negative	≥2 Organisms (≥1 non-uropathogen)	Any colony count
	Negative	Mixed bacterial flora ^e	≥100,000 CFU/mL
Insignificant Growth	Positive or negative	1 Non-uropathogen	≤10,000 CFU/mL
	Negative	1 Non-uropathogen	≤100,000 CFU/mL

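### Infants whose clean catch fails are removed after randomization, in that arm only, which tilts parental satisfaction (a primary endpoint) and procedure duration towards clean catch

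*Protocol*

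**What the plan says.** Protocol section 19 deals with an unsuccessful clean catch. The subject who "failed urine collection by CCU , will be removed from study and counted as CCU collection failure" then leaves the trial's procedures: "After that to be managed by in-charged doctor as per the treating doctor plan". The rule names clean catch only. Nothing in the protocol says what happens when a catheterization fails.

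Section 7 places randomization at triage, before any collection attempt.

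Section 6 lists the main outcomes as "Primary endpoints: Urine culture contamination rate and parental satisfaction", with pain score and duration secondary. According to the Summary (Clinical Measurement), the pain score and "parental satisfaction survey will be filled at the time of the procedure", and duration is taken by stopwatch.

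The appendix on the clean catch technique states: "Success is defined as the collection of a sample within 5 min of starting the stimulation maneuvers". The step before it says: "Both stimulation maneuvers are repeated until micturition starts".

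On size, section 6 says: "A pilot study with 40 samples in each arm will be conducted". Section 18 names the t test, Mann-Whitney and chi-square tests. It does not bring removed infants back into any comparison.

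**The concern.** Removal happens after randomization, depends on how the assigned procedure turned out, and applies to one arm. The groups compared are then no longer the groups randomized. The clean-catch arm is reduced to infants in whom the technique worked, while the catheter arm keeps everyone.

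Contamination can only be judged where there is a specimen, so some selection there is unavoidable and this point does not rest on it. Satisfaction, pain and duration are different. Each exists for a failed attempt, and a parent whose infant was stimulated without result can still say whether they were satisfied. Counting the failure gives a success rate but does not return these infants to the three comparisons.

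The likely direction matches the result the protocol anticipates in section 22, namely higher satisfaction with clean catch. Section 17 speaks of replacing catheterization in local guidelines, so a difference produced by the exclusion rule could be read as support for a change in practice.

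**Working it through.** **Inputs from the protocol.** Clean-catch success rates *s* in section 3: 90%, 86.3% and 61%. The protocol comments on the last that it was "possibly due to patients with a low oral intake that were not excluded from the study". Number per arm: 40 (section 6). Success limit: 5 minutes = 300 s (appendix). The 40 comes from no stated calculation, so there is no figure of the plan to reproduce first.

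**Assumed inputs.** The documents give no satisfaction rates. I take 90% satisfied after a successful catch and a proportion *f* after a failed one, with *f* from 20% to 50% as the main range and 70% and 90% also shown. Section 18 prints its significance threshold as 0.05%; I use 5%, two-sided.

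**Infants removed.** 40 × (1 − *s*) = 4.0, 5.5 and 15.6, leaving 36.0, 34.5 and 24.4. If the 40 means specimens obtained, the number to randomize is 40/*s* = 44.4, 46.3 and 65.6, rounded up to 45, 47 and 66.

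**Bias in satisfaction.** Satisfaction among all randomized is *s* × 0.9 + (1 − *s*) × *f*. Among successes only it is 0.9. The overstatement is (1 − *s*) × (0.9 − *f*).

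**False positives.** Catheter satisfaction was set equal to true clean-catch satisfaction over all randomized, with 40 randomized per arm, clean-catch failures removed and an uncorrected chi-square test applied. At least 100,000 trials were simulated per setting. The last column is the share of trials significantly favouring clean catch.

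| *s* | *f* | Overstatement (points) | False result favouring clean catch |
|---|---|---|---|
| 90% | 20% | 7.0 | 13% |
| 90% | 50% | 4.0 | 7% |
| 90% | 70% | 2.0 | 4% |
| 86.3% | 20% | 9.6 | 20% |
| 86.3% | 50% | 5.5 | 10% |
| 86.3% | 70% | 2.7 | 5% |
| 61% | 20% | 27.3 | 71% |
| 61% | 50% | 15.6 | 32% |
| 61% | 70% | 7.8 | 11% |

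At *f* = 90% the overstatement is 0. With failures kept in their arm, the false-favourable share is about 2.5–3% throughout.

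**Duration.** Assume exponential waiting time to a caught sample, with rate λ set so that a proportion *s* succeed by 300 s: λ = −ln(1 − *s*)/300. The median over all randomized is ln 2/λ. The median among successes solves 1 − exp(−λt) = *s*/2.

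| *s* | Median, all randomized | Median, successes only |
|---|---|---|
| 90% | 90 s | 78 s |
| 86.3% | 105 s | 85 s |
| 61% | 221 s | 116 s |

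**The case against.** **Removal may not mean exclusion from analysis.** Section 19 concerns what happens to the infant, and forms completed during the attempt may already exist. This is possible. But the sentence takes the infant out of the study and keeps only a failure count, and handover to the treating doctor is covered separately in the next sentence. A statistical analysis plan could restore these infants only by contradicting section 19. If handover was all that was meant, the wording still needs changing.

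**Not every failure is a long attempt.** An infant may void early and the urine be missed. This stands. The exponential model treats every failure as no void by 300 s, so its medians are illustrative. The tendency towards shorter recorded times remains, because no attempt beyond 5 minutes counts as a success.

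**The satisfaction gap is assumed.** This also stands. With 70% satisfied after failure, the false-favourable share drops to 4–5% at 86–90% success and 11% at 61%. The protocol also recommends a catheter sample after a successful clean catch (sections 8 and 11), which could narrow the gap.

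**The 61% rate may not apply.** The protocol links it to poor oral intake, and this trial checks feeding beforehand. The 86–90% rows are therefore the more relevant ones. There the duration shift is 12–20 s, and the data sheet records minutes.

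**It is a pilot and failures are counted.** The success rate does stay visible. But satisfaction is declared primary and significance tests are planned.

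These arguments reduce the size of the effect. None removes the one-sided exclusion.

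**Conclusion.** The concern holds. As written, section 19 removes randomized infants because of the result of their assigned procedure, in the clean-catch arm only, and so biases the comparison of a primary endpoint. This is a rule that the protocol fixes badly, not a detail left to a later document.

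The exclusion is certain on the plain wording; its size is not. At 86–90% success the satisfaction overstatement is about 4–10 points under the main assumptions, about 2–3 points if 70% of parents are satisfied after a failure, and nil if failure makes no difference. At 61% it is 16–27 points, with the protocol's own reservation about that rate. Recorded clean-catch time is shifted downwards, by an amount that depends on the waiting-time assumption. Pain is subject to the same selection, but its direction cannot be established from the documents.

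The change should be made before further enrolment, because outcomes not recorded at a failed attempt cannot be recovered later.

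**What to change.** **Core change.** Replace the removal sentence in section 19 with: *Infants with failed collection stay in their randomized arm for satisfaction, pain and duration, recorded at the end of the assigned attempt and before any second collection.* Apply the same to failed catheterizations.

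**Analysis (section 18).** For duration, either censor failed attempts at the end of the attempt and use a log-rank test, or rank them worst and use Mann-Whitney. Report the success rate by arm. Report contamination per culture obtained, together with the share of all randomized infants who yielded an uncontaminated specimen by the assigned method.

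**Clarifications.** These do not carry the finding but belong in the same edit:
- Reconcile the 5-minute definition of success with the instruction to continue until voiding starts, and state how a sample obtained after 5 minutes is classified.
- State when the recorded duration begins.
- State whether the 40 in section 6 counts infants randomized or specimens obtained.
- Add assigned arm and success or failure to the data collection sheet. It currently records only the method used.

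**Cost.** Sections 6, 18 and 19 are reworded and two boxes are added to the sheet. Clean-catch results will look less favourable. If 40 means infants randomized, about 36, 35 or 24 clean-catch cultures will be available for the contamination comparison at the three success rates. If it means specimens, 45, 47 or 66 infants must be randomized to clean catch. The change affects what is recorded and analysed, not how the infant is managed.
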